### 5.8.1 **Procedures for discontinuation of a patient from the study**

Patients are at any time free to withdraw from the study without prejudice to further treatment (withdrawal of consent). Such patients will always be asked about the reason(s) and the presence of any adverse events. If possible, they will be seen and assessed by an investigator(s). Adverse events will be followed up (see Sections 6.4.3 and 6.4.4); the eDiary/home spirometry device, investigational product and additional non-investigational study drugs should be returned by the patient.

For patients discontinuing during the enrolment period or run-in period, only assessment for AEs will be performed. The reason for discontinuation should be recorded in the eCRF.

If a patient discontinues participation in the study due to study specific discontinuation criteria no 8 to 11, this should always be recorded as "study specific discontinuation criteria met" on the termination form. In addition, the investigator has to assess whether the discontinuation should also be reported as a discontinuation due to adverse event (DAE) on the AE form.

If a patient discontinues after randomisation he/she should be asked to attend the end of treatment visit, Visit 6, and the follow-up visit, Visit 7. All assessments should be carried out at these visits unless the patient is unwilling to do so, with the exception of MSCT for patients who have had less than 2 months of randomised treatment. The reason for discontinuation will be recorded in the eCRF.

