To be randomised to the 12-week treatment period a visually acceptable MSCT scan with no clinically relevant abnormal CT findings must have been performed 2 to 7 days before Visit 2. Before the patient has the baseline MSCT scan the laboratory safety results from Visit 1b must be reviewed and considered eligible (refer to exclusion criterion 8). The patient must also show complete morning recordings of daily FEV1 data at least 10 of the last 14 days before Visit 2.

At Visit 2 eligible patients will be randomised to either

- AZD9668, 60 mg twice daily
- placebo to match AZD9668

Two weeks after stopping study medication there will be a follow up visit.

An independent safety review committee will review available safety data, see Section 12.4.

The pharmacogenetic part of the study is described in Appendix D.

Clinical Study Protocol Drug Substance AZD9668 Study Code D0520C00014 Edition Number 1 Date

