# (Continued)

Table 1	Visit schedule	(Continued)
Visit No.	Type of Visit	No. of weeks ± no of days between visits
5	Treatment visit	8 weeks $\pm 3$ days after Visit 2
6	End of treatment visit	12 weeks -3 days after Visit 2
7	Follow-up Visit	14 weeks ±3 days after Visit 2

Study Visit	Visit 1a	Visit 1b	Visit 2	Visit 3	Visit 4	Visit 5	Visit 6	Visit 7
Written informed consent	х							
Demography (date of birth, sex and race)	X							
Physical examination		х	Х	Х	Х	х	Х	Х
Height/Weight		X					x (weight only)	
Medical/surgical history		х						
COPD history		X						
Smoking history		X						
Smoking habits			Х				X	
MSCT (pre-visit, see Section 6.3.1)			2 to 7 days before Visit 2				0 to 3 days before Visit 6	
Clinical chemistry, haematology and urinalysis b		X	Х	Х	х	X	X	Х
Pregnancy test a		х	Х					х
Inclusion/exclusion criteria	х	х	Х					
Randomisation			х					
Vital signs, 12-lead ECG b		х	x c	Х	Х	х	х	х
Spirometry (FEV 1 , FVC, SVC) b		Х	Х	Х	Х	Х	Х	
Body Plethysmography (IC, TLC, FRC, RV, SGaw) b			X				X	
DL CO b			Х				Х	
Dispense maintenance and reliever drugs	(x)	X	(x)	(x)	(x)	(x)		

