#### Table 2Study Plan

### (Continued)

Table 2

Study Visit	Visit 1a	Visit 1b	Visit 2	Visit 3	Visit 4	Visit 5	Visit 6	Visit 7
Administer AZD9668 morning dose at clinic after spirometry			Х	х	x	х	х	
AZD9668/placebo Dispense/ Check/ Return (d/c/r)			d		d / c / r	d / c / r	c / r	
e-PRO / Home spirometry device d training/ dispense/ check/ return (t / d / c / r)	(t)	t / d	С	С	с	С	c / r	
BCSS, EXACT, FEV 1 , PEF and intake of study drugs - assessed at the patient's home		x					X	
SGRQ-C b		(x) e	Х				Х	
Desmosine urine sampling			Х		Х		Х	
Concomitant medications recorded	Х	Х	Х	Х	Х	Х	Х	Х
Adverse events		Х	Х	Х	х	х	х	Х
Exacerbation recording		X	Х	Х	X	Х	Х	X
Pharmacogenetics blood sampling (optional) f			Х					

a Pregnancy tests at Visit 1b and 7 to be taken in blood and pregnancy test at Visit 2 to be taken in urine.

b Assessments to be done pre-dose of AZD9668 at Visits 2-6.

c A second ECG and vital signs measurement should be done 3-4 hours post-dose of AZD9668 at Visit 2.

d ePRO including BCSS and EXACT questionnaires, Questions on intake of study drugs and Spirometry measurements of PEF and FEV1,

e Training session, data not to be collected in study database.

f Only 1 pharmacogenetic sample is required. This should be taken at Visit 2 or any subsequent visit once separate written informed consent has been obtained.

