### 6.4.5 Laboratory safety assessment

Blood and urine samples for determination of clinical chemistry, haematology, and urinalysis will be taken at the visits indicated in the Study Plan (see Table 2) and before intake of the morning dose of investigational product. Blood samples will be analysed at a central laboratory. Urinalysis will be performed locally at the study site using dipsticks provided by the central laboratory.

The central laboratory will provide all the materials required for blood and urine sampling. Instructions for labelling, storage and shipping will be detailed in the laboratory manual. The central laboratory will also provide up to date reference ranges throughout the study for the management of patient safety.

Clinically relevant deviations from the reference range in the lab values will be handled as outlined in Section 6.4.3, adverse events based on examinations and tests.

The following laboratory variables will be measured:

Haematology		
Haemoglobin	Mean Cell Volume (MCV)	Platelet count
Erythrocyte count	Mean Cell Haemoglobin (MCH)	Reticulocyte count
Haematocrit	Mean Cell Haemoglobin Concentration (MCHC)	Leucocyte count (absolute and percentage including neutrophil, lymphocyte, monocyte, eosinophil and basophil counts)

Clinical Chemistry			
Creatinine	Potassium	Creatinine kinase (CK) a	
C-Reactive Protein (CRP)	Calcium, total Lactate dehydroger		
Total bilirubin b	Sodium Glucose		
Alkaline phosphatase	Cholesterol	Free thyroxine (T4) (Visit 1b only)	
Aspartate aminotransferase (AST)	Triglycerides	Thyroid stimulating hormone (TSH) (Visit 1b only)	
Alanine aminotransferase (ALT)	Urea	Haptoglobin	
Albumin	Gamma Glutamyltransferase (GGT)	hCG c	

a CKMB fraction to be measured if CK is elevated >2 x ULN (as detailed in the laboratory manual)

b Unconjugated and conjugated bilirubin will be measured if the total bilirubin is elevated

c Visit 1b and Visit 7, only for female patients

For blood volumes see Section 7.1.

Urinalysis		
Protein	Glucose	Haemoglobin

Please refer to Section 5.8 for the discontinuation criteria relating to laboratory safety variables.

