### 6.4.9 Pregnancy testing

A pregnancy test (blood sample) will be collected from all women at Visits 1b and 7.

In addition a urine pregnancy test will be performed on women of child bearing potential at Visit 2. The study personnel at the centre will analyse urine from a mid-stream urine sample using dipsticks provided by the central laboratory. The result will be recorded in the eCRF. See Section 13.3 for reporting procedures if pregnancy should occur during the course of the study.

Clinical Study Protocol Drug Substance AZD9668 Study Code D0520C00014 Edition Number 1 Date

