### **13.3.1** Maternal exposure

If a patient becomes pregnant during the course of the study the investigational product should be discontinued immediately.

Pregnancy itself is not regarded as an adverse event unless there is a suspicion that the investigational product under study may have interfered with the effectiveness of a contraceptive medication. Congenital abnormalities/birth defects and spontaneous miscarriages should be reported and handled as SAEs. Elective abortions without complications should not be handled as AEs. The outcome of all pregnancies (spontaneous miscarriage, elective termination, ectopic pregnancy, normal birth or congenital abnormality) should be followed up and documented even if the patient was discontinued from the study.

If any pregnancy occurs in the course of the study, then investigators or other site personnel inform appropriate AstraZeneca representatives **within 1 day** ie, immediately but no later than the **end of the next business day** of when he or she becomes aware of it. The designated AstraZeneca representative works with the investigator to ensure that all relevant information is provided to the AstraZeneca Patient Safety data entry site within 1 or 5 days for SAEs, see Section 6.4.4 and within 30 days for all other pregnancies

The same timelines apply when outcome information is available.

The PREGREP module in the eCRF is used to report the pregnancy and the PREGOUT is used to report the outcome of the pregnancy.

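### Section 5.8.1 does not exempt patients discontinued for pregnancy from the Visit 6 MSCT once they have had 2 months or more of treatment

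*Protocol*

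**What the plan says.** **Discontinuation rule.** Protocol Section 5.8 lists pregnancy as reason 6 for discontinuing a patient. Section 5.8.1 then says what follows: "If a patient discontinues after randomisation he/she should be asked to attend the end of treatment visit, Visit 6", and also Visit 7. All assessments are to be done at these visits unless the patient is unwilling, "with the exception of MSCT for patients who have had less than 2 months of randomised treatment".

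**Action on pregnancy.** Section 13.3.1 says: "If a patient becomes pregnant during the course of the study the investigational product should be discontinued immediately". It goes on to reporting and follow-up of the outcome and does not mention MSCT. Section 6.3.1, which describes the scans, has no pregnancy exemption either.

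**Radiation rationale.** Section 1.4 places pregnancy in the group at higher radiation risk, notes that participation may bring the patient no direct benefit, and applies the ALARA principle.

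**Pregnancy tests.** Table 2, footnote a: "Pregnancy tests at Visit 1b and 7 to be taken in blood and pregnancy test at Visit 2 to be taken in urine". The laboratory table in Section 6.4.5 limits hCG to "Visit 1b and Visit 7, only for female patients". Section 6.4.9 restricts the Visit 2 urine test to women of child-bearing potential.

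**Scan timing.** Table 2 places the second MSCT "0 to 3 days before Visit 6". For the first scan, Section 3.1 adds a gate: "Before the patient has the baseline MSCT scan the laboratory safety results from Visit 1b must be reviewed and considered eligible".

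**The concern.** Section 5.8.1 contains an exception written for MSCT alone, and that exception covers only short exposure to treatment. The patient whom the protocol's own radiation section singles out is left under the general rule that all assessments be carried out. A site that follows the text as written would ask a patient known to be pregnant to have an inspiratory and expiratory CT pair.

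A related and weaker point is that an unrecognised pregnancy would not be looked for before the second pair. The last scheduled test is at Visit 2 and the next one comes after the scan.

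What is at stake is avoidable fetal radiation exposure in a study that may not benefit the participant. This is a safety and procedure matter. It has no bearing on the statistical conclusions.

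**Working it through.** The main point is settled by reading the sections together. The secondary point needs only calendar arithmetic.

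**1. Does any text exempt a pregnant patient from the second MSCT?**

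| Place | What it does on pregnancy | Exempts from MSCT? |
|---|---|---|
| Section 4.3, criterion 13 | Excludes at entry | Not applicable after randomisation |
| Section 5.8, reason 6 | Ground for discontinuation | No |
| Section 5.8.1 | MSCT exception only for under 2 months of treatment; unwillingness excuses any assessment | No |
| Section 6.3.1 | Silent | No |
| Section 13.3.1 | Stops investigational product; reporting | No |
| Section 1.4 | Names pregnancy as higher risk; ALARA | States a principle, no operative rule |

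The operative text therefore gives no exemption at 2 months or more. Discontinuation for risk to the patient (Section 5.8, reason 3) does not help, because it is a ground for stopping and the Visit 6 request follows from stopping.

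**2. Who could be affected?** Section 4.1 admits women of child-bearing potential. Women over 57, and women over 50 who have been amenorrhoeic for 12 months or more, count as post-menopausal. What remains is women aged 50 to 57 who meet neither that definition nor the surgical-sterility definition. The protocol does not say how many are expected.

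**3. Where do the tests fall relative to the scans?** Days are counted from Visit 2, using Table 1 for visits and Table 2 or Section 6.3.1 for scans.

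- Visit 6: 12 weeks, minus up to 3 days = 84 − 3 to 84 = day 81 to 84.
- Second MSCT: 0 to 3 days earlier = 81 − 3 to 84 − 0 = day 78 to 84.
- Last scheduled test before it is at Visit 2, so the gap is 78 to 84 days.
- Visit 7: 14 weeks ± 3 days = 98 − 3 to 98 + 3 = day 95 to 101.
- Next scheduled test after the scan: 95 − 84 = 11 days at the shortest, 101 − 78 = 23 days at the longest.
- Scheduled tests between Visit 2 and the second scan: none.

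**4. Comparison with the baseline scan.** Visit 1b is 14 to 17 days before Visit 2, and the baseline scan is 2 to 7 days before Visit 2. The Visit 1b serum hCG is therefore taken 14 − 7 = 7 to 17 − 2 = 15 days before that scan, and the laboratory results must be reviewed first. The baseline pair is covered, and the second pair has no equivalent check in the protocol.

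The day 78 to 84 figure applies to patients on schedule. Section 5.8.1 does not date Visit 6 for early discontinuers, so their gap from the Visit 2 test may be shorter, still with no scheduled test in between.

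**The case against.** The strongest reply is that Section 5.8.1 is a general rule for retrieving data after discontinuation, that it is silent on pregnancy, and that silence is not an instruction to scan. The patient is only to be asked and may decline. A pregnancy must reach the sponsor within 1 day, so both investigator and sponsor would know. ALARA and the GCP and Helsinki commitments in Section 8.1 also apply. Much of this stands: a CT in a known pregnant patient would be very unlikely. It does not correct the rule, however. Section 5.8.1 tells sites to carry out all assessments, names one MSCT exception and omits this one. Leaving the patient to refuse puts the burden in the wrong place.

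The design also limits the risk at source, through entry from age 50, mandatory highly effective contraception (Section 5.1), and negative tests at Visits 1b and 2. This stands in full and is why the point is minor.

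On test timing, Section 6.3.1 refers to a separate manual said to hold all necessary MSCT instructions. That manual is not among the documents, and a check before scanning could sit there. This also stands, so the test schedule can only be a conditional, secondary suggestion.

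A reader might infer more than the documents support:

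- **That pregnant patients would in practice be scanned.** The safeguards above make that improbable.
- **That the baseline scan is unprotected too.** The Visit 1b laboratory review covers it.
- **That the stretch of treatment during which the missing exemption could apply measures the risk.** It measures calendar time only and says nothing about the probability of exposure.

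**Conclusion.** The point holds as a wording defect in Section 5.8.1. For patients discontinued after 2 months or more, the rule asks for the Visit 6 MSCT and does not exempt those discontinued for pregnancy, which sits badly with the radiation rationale in Section 1.4. This rests on the protocol text alone.

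The absence of a pregnancy test between Visit 2 and the second scan is a fact of the schedule: 78 to 84 days before the scan and 11 to 23 days after it for on-schedule patients. Whether it is a gap in practice depends on the unseen MSCT manual. If the manual requires a check, this part falls away and only the Section 5.8.1 wording remains.

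The size is very small. The number of women of child-bearing potential is not given and may be zero. No endpoint, sample size or analysis changes. The correction is optional and of low severity.

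**What to change.** **Main change.** In Section 5.8.1, add the words *or who are pregnant* to the end of the existing MSCT exception, so that it covers patients with under 2 months of randomised treatment and pregnant patients alike. The cost is one clause. The only data lost would be the Visit 6 MSCT of a pregnant patient, which should not be collected anyway.

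**Optional addition, unless the MSCT manual already requires it.** In Table 2 and Section 6.4.9, add one urine test before the second MSCT, for women of child-bearing potential only. Section 6.4.9 already provides for the method at Visit 2: "The study personnel at the centre will analyse urine from a mid-stream urine sample using dipsticks provided by the central laboratory". Because the scan may precede Visit 6 by up to 3 days, the dipstick has to be available when the patient attends for the scan. A positive result would cancel the scan, and discontinuation reason 6 would apply. The cost is one dipstick per such woman.

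The existing tests at Visits 1b, 2 and 7, the baseline scan procedure and the scan settings can stay as they are.

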# 6. COLLECTION OF STUDY VARIABLES

# 6.1 Recording of data

The Rave Web Based Data Capture (WBDC) system will be used for data collection and query handling. Trained site personnel will be responsible for entering data on the observations, tests and assessments specified in the protocol into the WBDC system and according to the eCRF Instructions. The eCRF Instructions will also guide the study site in performing data entry. Data entered in the WBDC system will be immediately saved to a central database and changes tracked to provide an audit trail. The data will then be Source Data Verified (SDV), reviewed/queried and updated as needed. The data will be validated as defined in the Data Management Plan. The investigator will ensure that data are recorded on the eCRF as specified in the study protocol and in accordance with the instructions provided.

The investigator ensures the accuracy, completeness, and timeliness of the data recorded and of the provision of answers to data queries according to the Clinical Study Agreement. The investigator will sign the completed eCRF. A copy of the completed eCRFs will be archived at the study site.

At clinic visits patients will enter data on paper questionnaires (SGRQ-C) and these data will be entered into the eCRF by the site personnel.

Patients will enter diary data and perform peak expiratory flow (PEF) and forced expiratory volume in 1 second (FEV1) measurements twice daily in a electronic diary/home spirometry device at home between visits. At Visit 1b all patients will be carefully instructed and trained in how to fill in the eDiary, how to blow PEF and FEV1 and how to handle the device. Written instructions will be provided to the patient in their local language.

# 6.2 Data collection and enrolment

In order to include eligible patients the investigator will be asked to screen patients based on:

- Age
- COPD history and current prescribed COPD medication
- Smoking history

• Concomitant medications and medical history.

At Visit 1a (enrolment visit), patients will sign the informed consent form prior to any study procedure or restriction being applied and will be assigned a unique enrolment code (see Section 5.2). The following data will be recorded in the eCRF:

• Date of birth, sex and race

At Visit 1b patients will be evaluated for eligibility to enter the study. The procedures to be followed are listed in the Study Plan, (Table 2) and the following data will be captured in the eCRF:

- COPD history including exacerbation history, date of diagnosis according to GOLD 2008 and current prescribed COPD medication (including 4 weeks preceding Visit 1b)
- Medical and surgical history relevant for the purpose of the study and current prescribed medication (including 4 weeks preceding Visit 1b)
- Smoking history
- Weight and height
- Physical examination
- Vital signs (pulse and blood pressure)
- 12-lead ECG
- Spirometry, pre- and post- bronchodilator FEV1, forced vital capacity (FVC) and slow vital capacity (SVC)
- Urinalysis
- Exacerbation recording
- Adverse events
- Dispensing of maintenance and reliever medication
- Check of inclusion/Exclusion criteria.

Height will be measured in cm (without shoes) and weight in kg (light clothes and without shoes).

The evaluation of pack years is described in the eCRF.

After evaluation of the laboratory safety variables and 2 to 7 days before Visit 2 eligible patients should be assessed by MSCT scanning.

### 6.2.1 Follow-up procedures

The procedures to be followed at the follow-up visit, Visit 7, are listed in the Study Plan, (Table 2).

# 6.3 Efficacy

The efficacy variables collected in the study are detailed in the sections below.

### 6.3.1 MSCT variables

A baseline MSCT assessment (paired inspiratory and expiratory scan) will be performed 2 to 7 days prior to randomisation (Visit 2) to assess airway wall thickness, lung density and expiratory air trapping. The scan will be done after evaluation of the laboratory safety results from Visit 1b and it will be visually evaluated by a radiologist within 48 hours and prior to randomisation. The scan must be visually acceptable with no artefacts related to motion or streak or metal. If any defects are noted they will be recorded in the CRF and may result in loss of scan and patient. A second assessment will be performed at 0 to 3 days prior to Visit 6.

The performance of each site and scanner will be assessed before the first patient is enrolled.

All sites will be provided with a separate manual containing all necessary instructions for MSCT assessments.

Images will be transferred to a core lab at a CRO for analysis. Images will be analysed by VIDA software and the baseline scans will be double-read for quality check.

### Equipment

Scanners that meet or exceed the study protocol with volumetric scan capabilities and at least 16 detectors will be used for MSCT scanning. The CRO and monitor are responsible to ensure appropriate equipment is available for scanning. During the course of the study sites are recommended not to change the scanners. No contrast agent will be used. If possible the same radiographer should perform all examinations.

## Calibration

The scanners will be calibrated on a daily basis using air and water calibration. The calibration data will be evaluated by site and periodic reports may be requested by the

sponsor. To ensure cross-site standardization a specific phantom will be circulated to the sites in the set-up phase to obtain phantom scans. Detailed instructions (protocol settings, reconstruction parameters etc.) for the phantom will be included in a separate MSCT manual.

### Measurements/Conditions

Detailed instructions on the imaging protocol are defined in the MSCT scan protocol. The MSCT scan will be done at full expiration and full inspiration. The patients will be trained on breath holding few times before the actual scan is taken. No respiratory or cardiac gating will be used. Following the procedure the patient can leave the scanning area and no medical check-up will be needed at the end of the scanning procedure. During the procedure the patient is asked not to move, as any significant movement can affect scan quality. The entire scan process is expected to take approximately 30 mins.

